8.3.3. Acclimatization

Before each visit the volunteer will get acclimatized under relax conditions for at least 10-15 min.

8.4. Self assessment questionnaire (subjects' judgment)

At T2 each volunteer fills a questionnaire regarding:

- the efficacy of the study treatment on acne scars (score: very marked; marked; medium; light; absent);
- the treatment tolerance (score: bad; poor; medium, good; excellent).

9. TOLERANCE

9.1. Tolerance evaluation

Product tolerance will be evaluated considering:

- local expected events/reactions induced by the micro-injection (tardive swelling, pain, erythema, bruise)
- any other adverse event/reaction, also of systemic source occurred during the study

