1. AIM OF THE STUDY

Aim of the study is to evaluate the efficacy and the safety of the deep injection of Profhilo Structura® in acne scars of the face (ice picks, rolling, boxcars).

It is also aim of this study to evaluate volunteer's satisfaction with the treatment effects and physicians satisfaction with the study products use.

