4.1. Study plan

Open clinical trial, conducted by 1 center under dermatological control.

3 visits will be performed during the study:

- T0 (baseline) clinical and instrumental evaluations, followed by the 1st injection procedure
- T1 (1 month after the 1st injection procedure) clinical and instrumental evaluations, followed by the 2nd injection procedure
- T2 (3 months after the 2nd injection procedure) clinical and instrumental evaluations.

DermIng S.r.l., Clinical Research and Bioengineering Institute [name] [contact]– www.derming.com

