4.2. Experimental design

The 1st treatment will be performed during T0 visit, after the basal evaluations planned by the study procedure. Treatment of acne scars of the face by using a subcision+injection technique: the needle (25 G) or cannula (25 G) (wider areas are treated with the cannula) is inserted into the skin and made to move with a back-and-forth motion in order to detach scar collagen bundles. Then the product is injected. The 2nd treatment will be performed after 4 weeks (1 month from T0). Results of the study will be elaborated after the completion of the clinical phase.

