4.3. Investigators

The study will be conducted by and under the supervision of a dermatologist.

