9.2. Adverse event

9.2.1. Definition and classification

Adverse Event (AE): any untoward medical occurrence, unintended disease or injury, or any untoward clinical signs (including an abnormal laboratory finding) in subjects undergoing a clinical investigation, users or other persons which does not necessarily have a causal relationship with the product under investigation. AEs may manifest as new findings (signs, symptoms, diagnoses, laboratory results) or alterations in pre-existing conditions.

NOTE 1: This definition includes events related to the investigational device or the comparator.

NOTE 2: This definition includes events related to the procedures involved.

NOTE 3: For users or other persons, this definition is restricted to events related to investigational medical devices.

Adverse Device Effect (ADE): an Adverse Device Effect (ADE) is defined as adverse event related to the use of the investigational medical device.

Note 1: This definition includes any adverse event resulting from insufficiencies or inadequacies in the instructions for use, the deployment, the implantation, the installation, the operation or any malfunction of the investigational medical device.

Note 2: This definition also includes any event resulting from user error or from intentional abnormal use of the investigational medical device.

Serious Adverse Event (SAE): an Adverse Event that:

- a. Led to death,
- **b.** Led to a serious deterioration in health of subject, user, or others that: Resulted in a life-threatening illness or injury, or

DermIng S.r.l., Clinical Research and Bioengineering Institute [name] [contact]– www.derming.com

Resulted in persistent or significant disability or incapacity and/or permanent impairment of a body function or permanent damage to a body structure, or

Required in-patient hospitalization or prolongation of existing hospitalization, or

Resulted in medical or surgical intervention to prevent life threatening illness or injury or permanent impairment to a body structure or a body function.

Examples include allergic bronchospasm (a serious problem with breathing) requiring treatment in an emergency room, serious blood dyscrasias (blood disorders) or seizures/convulsions that do not result in hospitalization. The development of drug dependence or drug abuse would also be examples of important medical events.

c. Led to fetal distress, fetal death or a congenital abnormality or birth defect.

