The severity/intensity of adverse events/reactions can be graded either on a three-point scale:

DermIng S.r.l., Clinical Research and Bioengineering Institute [name] [contact]– www.derming.com

- Mild or Grade 1: discomfort noted, but no disruption to normal daily activities.
- Moderate or Grade 2: discomfort sufficient to reduce or affect normal daily activities.
- Severe or Grade 3: inability to work or to carry out normal daily activities.

Relationship with the tested product:

The investigator evaluates the cause-effect relation of each adverse event to the experimental product. Each AE will be classified according to 5 different levels of causality":

- not related
- unlikely
- possible
- probable
- certain

If there is insufficient or incomplete evidence to make a clinical judgment of the causal relationship, the causality can be evaluated as "not assessable". All adverse events judged by either the reporting Investigator or the sponsor as having a reasonable causal relationship to a medical device qualify as adverse device effects.

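### Tolerance rests on four named local reactions, but the visit lists never ask for them after either injection; the next listed record is generic, about 4 and 13 weeks later

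*Combined protocol and SAP*

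**What the plan says.** Safety is half of the primary aim: section 1 sets out to "evaluate the efficacy and the safety of the deep injection" of the product. Section 9.1 then gives tolerance two components. The first is "local expected events/reactions induced by the micro-injection (tardive swelling, pain, erythema, bruise"; the second is any other adverse event, including systemic ones.

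There are three visits. Section 4.2 fixes the first interval: "The 2nd treatment will be performed after 4 weeks (1 month from T0". Section 4.1 fixes the second: "T2 (3 months after the 2nd injection procedure) clinical and instrumental evaluations". Section 10 lists what is done at each visit:

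- **T0 (10.1):** consent, CRF entries, eligibility, assessments and profilometry, then the first injection. There is no adverse-event item.
- **T1 (10.2):** a general entry for adverse events and intercurrent illness comes first, then assessments and profilometry, then the second injection.
- **T2 (10.3):** the same general entry, assessments, profilometry and the volunteer questionnaire.

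That questionnaire (8.4) has one global tolerance item: "the treatment tolerance (score: bad; poor; medium, good; excellent". It names no reaction and asks for no date.

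Other sections set general duties. In the adverse-event definition of 9.2.1, "This definition includes events related to the procedures involved". Section 9.2.2.2 requires every event to be documented whatever its seriousness, and 9.2.2.2 and 9.2.3 require follow-up to resolution.

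**The concern.** A named outcome needs a named measurement at a time when it can be observed. Here the reactions that define tolerance are specific, while the scheduled items that could collect them are general and come weeks after the injection. The duty to document an event applies once someone has seen it or mentioned it. It does not make anyone look or ask.

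Three features make this more than a formality. First, one of the four reactions is described as tardive, so observation on the injection day cannot be relied on to catch it. Second, the severity scale is anchored to daily life, for example "Moderate or Grade 2: discomfort sufficient to reduce or affect normal daily activities", which cannot be fully judged while the subject is still at the site. Third, the reactions are labelled as expected, and a subject may not think an expected bruise worth mentioning a month or three months later.

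The study is open and describes no comparator, so the recorded frequency and grade are themselves the tolerance result. Reactions that go unrecorded move that result in one direction, towards better apparent tolerance.

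**Working it through.** The plan gives no figure of its own to reproduce here. The check is a reading of the visit lists against 9.1, plus a conversion of the intervals.

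**1. What is listed after each injection**

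| Injection | Position in the visit list | Adverse-event item after it, same visit | Next listed item | Names the four reactions? |
|---|---|---|---|---|
| 1st | last item at T0 (10.1) | none | T1 (10.2) | no |
| 2nd | last item at T1 (10.2) | none; the T1 item is listed first | T2 (10.3) | no |

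The order is not an accident of layout. Section 4.1 also places the evaluations before the injection at T0 and T1, and 4.2 puts the first treatment after the baseline evaluations.

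**2. Intervals**

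- First injection to T1: 4 weeks as stated in 4.2, which is 4 × 7 = 28 days. A calendar month would be 365.25 / 12 / 7 = 4.35 weeks.
- Second injection to T2: 3 months (4.1), which is 3 × 365.25 / 12 / 7 = 13.04 weeks, or about 91 days. By calendar it is 89 / 7 = 12.7 to 92 / 7 = 13.1 weeks; with 4-week months it would be 12.
- Consistency: 4 + 13.04 = 17.04 weeks, against the 4 months after the first procedure in 10.3, 4 × 365.25 / 12 / 7 = 17.39 weeks. The timings agree.

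The gaps are therefore about 4 and 13 weeks, with 2 generic items over the whole follow-up.

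**3. Whether anything else in the text fills the gap**

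- Clinical assessment (8.1) is scar grade. Profilometry and photographs (8.2.3) are described for efficacy.
- The CRF contents listed in section 6 do not mention local reactions.
- The text describes no diary, telephone contact, post-injection observation period or early visit.
- Sections 12.1 to 12.5 describe the analysis of clinical and instrumental data and specify no tolerance summary.

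**4. What will be caught anyway**

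Section 4.3 says "The study will be conducted by and under the supervision of a dermatologist", so reactions visible at the injection are likely to be noticed. Once noticed or reported, they must be documented, graded and followed. What remains exposed is any reaction that begins, worsens or resolves away from the site and is not volunteered.

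**The case against.** The strongest reply is that the deciding document cannot be seen. Section 9.2.2.2 sends every event to an adverse event form in the CRF, enclosed in the appendices. That form and the design figure in section 4 are not in the text. If the form already lists the four reactions with dates and grades, the fault is only a missing cross-reference. This stands as a limit: the point is about the visit lists, and it cannot be widened to say that no such field exists.

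A second reply is that visit lists are summaries. They do not name the photographs or the scar scale either, and the adverse-event item at T1 and T2 may be read together with 9.1. That is a fair reading of T1 and T2. It does not supply a record after the injection on either day, or shorten the intervals.

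A third reply is that the general recording duties suffice. They cover what is seen or reported, and nothing here says that reactions would go unrecorded altogether. They do not give uniform, solicited capture.

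Two stronger readings are tempting and are not supported:

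- **Comparison between injections.** A reader might infer from the unequal gaps that reaction counts after the first and second injections would be biased against each other. No such comparison is planned in 12.1 to 12.5, so this is not a fault in the plan.
- **A size for the loss.** A reader might want to assume reaction rates and recall at 4 and 13 weeks and compute a shortfall. The documents give no rate, onset, duration or recall for these reactions, and plausible assumptions include no loss at all. Such a figure would show only what was assumed.

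**Conclusion.** The point holds in a limited form. Section 9.1 makes four local reactions a tolerance outcome, and the visit lists contain no solicited, uniform record of them after either injection. The next listed item is generic and falls about 4 weeks after the first injection and about 13 weeks after the second. Capture in between depends on observation on the day, spontaneous report or recall.

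The direction of the effect is clear for an open study without a comparator: missed reactions lower the reported frequency and flatter the product. Its size cannot be derived from the documents. For reactions that are reported, follow-up to resolution is already required, so their duration is not at issue.

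The conclusion rests on two assumptions: that the unseen CRF form does not already ask about the reactions by name, and that the visit lists describe what sites will do. It is best treated as a cheap improvement, not as a flaw that undermines the study.

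**What to change.** 1. In 10.1 and 10.2, after the injection and before the subject leaves, add a record of the presence and provisional grade (the three-point scale in 9.2.1) of each of the four reactions.
2. Give a short reaction diary at T0 and T1, with onset, end and worst grade for each reaction, collected at T1 and T2.
3. At T1 and T2, ask about each of the four reactions by name, beside the existing general item.
4. In the SAP, state that frequency, worst grade and duration will be reported for each reaction.

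The minimum version is items 1 and 3 together. The check before departure is not enough alone, because it would miss tardive swelling and any change after the subject goes home. If the CRF form already collects this information, cite it in 10.1 to 10.3 and leave the rest.

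**Cost:** a few minutes at each visit, about 30 × 2 = 60 diary pages with data entry, a CRF revision, and a protocol amendment of which the Ethics Committee is to be informed (13.1). No extra visit is needed. Two drawbacks should be accepted openly: more mild reactions will be reported, and a diary kept for 13 weeks after the second injection may be filled in less well, which is why the named questions at T2 should stay even if the diary is used.

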9.2. Adverse event

9.2.1. Definition and classification

Adverse Event (AE): any untoward medical occurrence, unintended disease or injury, or any untoward clinical signs (including an abnormal laboratory finding) in subjects undergoing a clinical investigation, users or other persons which does not necessarily have a causal relationship with the product under investigation. AEs may manifest as new findings (signs, symptoms, diagnoses, laboratory results) or alterations in pre-existing conditions.

NOTE 1: This definition includes events related to the investigational device or the comparator.

NOTE 2: This definition includes events related to the procedures involved.

NOTE 3: For users or other persons, this definition is restricted to events related to investigational medical devices.

Adverse Device Effect (ADE): an Adverse Device Effect (ADE) is defined as adverse event related to the use of the investigational medical device.

Note 1: This definition includes any adverse event resulting from insufficiencies or inadequacies in the instructions for use, the deployment, the implantation, the installation, the operation or any malfunction of the investigational medical device.

Note 2: This definition also includes any event resulting from user error or from intentional abnormal use of the investigational medical device.

Serious Adverse Event (SAE): an Adverse Event that:

- a. Led to death,
- **b.** Led to a serious deterioration in health of subject, user, or others that: Resulted in a life-threatening illness or injury, or

DermIng S.r.l., Clinical Research and Bioengineering Institute [name] [contact]– www.derming.com

Resulted in persistent or significant disability or incapacity and/or permanent impairment of a body function or permanent damage to a body structure, or

Required in-patient hospitalization or prolongation of existing hospitalization, or

Resulted in medical or surgical intervention to prevent life threatening illness or injury or permanent impairment to a body structure or a body function.

Examples include allergic bronchospasm (a serious problem with breathing) requiring treatment in an emergency room, serious blood dyscrasias (blood disorders) or seizures/convulsions that do not result in hospitalization. The development of drug dependence or drug abuse would also be examples of important medical events.

c. Led to fetal distress, fetal death or a congenital abnormality or birth defect.

NOTE 1: This includes device deficiencies that might have led to a serious adverse event if

- a) suitable action had not been taken, or
- b) intervention had not been made, or
- c) if circumstances had been less fortunate.

NOTE 2: Planned hospitalization for pre-existing condition, or a procedure required by the Clinical Investigation Plan, without a serious deterioration in health, is not considered a SAE.

The term "life-threatening" in the definition refers to an event in which the subject was at risk of death at the time of the event; it does not refer to an event which hypothetically might have caused death if it was more severe.

Serious Adverse Device Effect (SADE): a Serious Adverse Device Effect (SADE) is an ADE that has resulted in any of the consequences characteristic of a serious adverse event.

Incident:

- a. any malfunction or deterioration in the characteristics and/or performance of a device, as well as any inadequacy in the labelling or the instructions for use which, directly or indirectly, might lead to or might have led to the death of a patient, or user or of other persons or to a serious deterioration in their state of health.
- b. Any technical or medical reason in relation to the characteristics or performance of a device for the reasons referred to in subparagraph (a), leading to systematic recall of devices of the same type by the manufacturer.

Device Deficiencies (DDs): any inadequacy of a medical device related to its identity, quality, durability, reliability, safety or performance, such as malfunction, misuse or use error and inadequate labelling. A malfunction is failure of an investigational medical device to perform in accordance with its intended purpose when used in accordance with the instructions for use or CIP. A use error is an act or omission of an act that results in a different medical device response than intended by the manufacturer or expected by the user (including slips, lapses, and mistakes). An abnormal use is an act or omission of an act by the operator or user of a medical device as a result of conduct which is beyond any means of risk control by the Manufacturer.

Unanticipated Serious Adverse Device Effect (USADE): Serious adverse device effect which by its nature, incidence, severity or outcome has not been identified in the current version of the risk analysis report.

Definition of the severity of an Adverse Event/Reaction:

The severity/intensity of adverse events/reactions can be graded either on a three-point scale:

DermIng S.r.l., Clinical Research and Bioengineering Institute [name] [contact]– www.derming.com

- Mild or Grade 1: discomfort noted, but no disruption to normal daily activities.
- Moderate or Grade 2: discomfort sufficient to reduce or affect normal daily activities.
- Severe or Grade 3: inability to work or to carry out normal daily activities.

Relationship with the tested product:

The investigator evaluates the cause-effect relation of each adverse event to the experimental product. Each AE will be classified according to 5 different levels of causality":

- not related
- unlikely
- possible
- probable
- certain

If there is insufficient or incomplete evidence to make a clinical judgment of the causal relationship, the causality can be evaluated as "not assessable". All adverse events judged by either the reporting Investigator or the sponsor as having a reasonable causal relationship to a medical device qualify as adverse device effects.

9.2.2 Categories of Adverse Events

Table 1. Categories of Adverse Events

ADVERSE EVENTS	Non-device-related	Device- or procedure-related	
Non-serious	Adverse Event (AE)	Adverse Device Effect (ADE)	
Serious	Serious Adverse Event	Serious Adverse Device Effect (SADE)	
	(SAE)	Anticipated	Unanticipated
		Anticipated Serious	Unanticipated Serious
		Adverse Device	Adverse Device Effect
		Effect (ASADE) 1	(USADE) ²

ASADE: is an effect which by its nature, incidence, severity or outcome has been identified in the IFU / Manual

9.2.2.2 AEs/Incidents reporting procedure

All incidents and adverse events (AEs) or adverse device effect (ADE) regardless the seriousness must be reported in the source file (if applicable) and in the "Adverse event form" (see "CRF" enclosed in Appendices section). Investigators are responsible for documenting adverse events in the eCRF section created for this purpose.

Moreover, the investigator must determine:

- (a) if the event is serious or not
- (b) if the event is related or not related to the study treatment.

Any adverse event, related or not related to the study treatment, must be documented and will be followed until completed resolution (see paragraph 8.2.3.).

Then, the investigator will decide to:

(a) interrupt definitively the study treatment

DermIng S.r.l., Clinical Research and Bioengineering Institute
[name]
 [contact]- www.derming.com
Test code
E0222

² USADE: is an effect which by its nature, incidence, severity or outcome has not been identified in the current version of the IFU /

- (b) continue the study as protocol directed
- (c) interrupt temporary the study treatment
- (d) end the study

In case a subject's withdraws from the trial, the form "End of Study" should be filled in and the reasons for discontinuation recorded. The withdrawal subject should be encouraged to attend the final visit for the last study assessment.

9.2.2.3 AEs submission

The investigator must immediately notify to Sponsor (IBSA) all Incidents/SAEs/SADEs occurred during the study by fax, or e-mail and within 24 hours of the investigator becoming aware of the event to the below dedicated contact details:

IBSA Drug Safety Unit (DSU) Telephone n.: [name]

Fax n.: [contact] / [name] Email: [contact]

using the Adverse Event MD form (Appendix 1) provided by the Sponsor.

The Sponsor will confirm the receipt of the concerned Incident/SAE to the investigator by e-mail within 48 hours after the first report was received.

Without acknowledgement of receipt of the e-mail, a letter with acknowledgement of receipt is also sent to the Sponsor accompanied by the form.

Day 0 is the day that the Sponsor receives a notification report from an Investigator and will be the reference to calculate the due date for reporting to the concerned Authorities.

The general provisions for reporting to the concerned Authorities by the Sponsor are into the MEDDEV 2.7/3 guideline.

According that the Sponsor must notified to Independent Ethics Committee, copying also Ministero della Salute:

- a) any SAE which indicates an imminent risk of death, serious injury, or serious illness and that requires prompt remedial action for other subjects, subjects, users or other persons or a new finding to it: immediately, without delay after awareness by Sponsor of a new reportable event or of new information in relation with an already reported event.
- Any other reportable events, or a new finding or update to it: immediately, but not later than 7 calendar days following the date of awareness by the Sponsor of the new reportable event or of new information in relation with an already reported event.

For the purpose of safety reporting within this study, National Laws must be taken into account and will be mandatory.

